### Exclusion criteria:

1. Pre-existing AKI
2. AKI within the last 3 months
3. End stage renal disease with dialysis dependency,
4. Kidney transplant

## 8 Statistical design and sample size calculation

The primary aim of the study is to estimate the incidence of post-surgery AKI and to derive the corresponding exact two-sided 95% confidence interval according to Clopper-Pearson. Depending on the type of surgery, AKI incidences of 1.8-39.3% are reported in existing literature (Table 2). As the width of the confidence interval increases, the closer the observed incidence of post-surgery AKI equals 50%, a rate of 40% is assumed, as a conservative approach. Using this assumption, the width of the confidence interval based on a sample size of  $n = 10,000$  patients and a confidence level of 95% is given by 0.019.

Thus, with  $n = 10,000$  patients, the incidence of post-surgery AKI can be estimated with at least this precision.

The study also aims to detect factors that might be correlated to the occurrence of post surgery AKI for different types of surgical procedures (e.g. cardiac, neurological etc.). Therefore, further exploratory analyses such as uni- and multivariable logistic regression analyses will be conducted. Given the relatively large number of different types of surgeries, a sample size of  $n = 10,000$  patients is sufficient to investigate the influence of this

parameters on the occurrence of post-surgery AKI in a uni- and multivariable context and to conduct corresponding subgroup analyses (e.g. cardiac surgery induced AKI).

Study	Year	Design	Population (n)	Definition	Incidence (%)
AKI after major abdominal surgery					
Armstrong et al. 	2009	Retrospective	Hepatobiliary (1535)	AKIN/ SCr	5.1
Bell et al. 	2014	Interrupted time series analysis	Major abdominal/GI (3271)	KDIGO/ SCr	9.8
Bihorac et al. 	2009	Retrospective	Major abdominal/GI (2337)	RIFLE/ SCr	39.3*
Biteker et al. 	2014	Prospective	Major abdominal/GI (510)	RIFLE/ SCr and GFR	7.1*
Brunelli et al. 	2012	Retrospective	Major abdominal/GI (1912)	AKIN/ SCr	26.8*
Causey et al. 	2011	Retrospective	Colorectal (339)	RIFLE/ SCr	11.8
Chao et al. 	2013	Retrospective	Major abdominal/GI (1972)	AKIN/ SCr	20.2
Cho et al. 	2014	Prospective	Hepatobiliary (111)	AKIN/ SCr and UO	1.8*
Coca et al. 	2010	Retrospective	Major abdominal/GI (11460)	AKIN/ SCr	18.9*
Correa-Gallego et al. 	2015	Retrospective	Hepatobiliary (2116)	RIFLE/ GFR	15.9
Grams et al. 	2016	Retrospective	Major abdominal/GI (44597)	KDIGO/ SCr	13.2*
Kambakamba et al. 	2015	Retrospective	Hepatobiliary (829)	AKIN/ SCr	8.2
Kim et al. 	2013	Retrospective	GI (4718)	KDIGO/ SCr	14.4
Lee et al. 	2014	Retrospective	GI (595)	AKIN/ SCr	35.3
Slankamenac et al. 	2009	Retrospective	Hepatobiliary (569)	RIFLE/ SCr and UO	15.1
Sun et al. 	2015	Retrospective	Major abdominal/GI (1345)	AKIN/ SCr	9.7
Sun et al. 	2015	Retrospective	Major gynaecological (865)	AKIN/ SCr	3.1
Teixeira et al. 	2014	Retrospective	Major abdominal/GI (450)	KDIGO/ SCr and UO	22.4
Tomozawa et al. 	2015	Retrospective	Hepatobiliary (642)	AKIN/ SCr	12.2
Vaught et al. 	2014	Retrospective	Major gynaecological (2341)	RIFLE/ SCr	12.6*

Abbreviations: AKIN, Acute Kidney Injury Network; GFR, glomerular filtration rate; GI, gastrointestinal; KDIGO, Kidney Disease: Improving Global Outcomes; RIFLE, Risk Injury Failure, Loss and End-stage; SCr, serum creatinine; UO, urine output

\* Patients with chronic kidney disease excluded

Table 2: Summary of epidemiologic studies used for sample size planning.

## 9 Timing of the statistical analysis

The statistical analysis will be performed after data entry into the study database and data cleaning has been completed.

## 10 Analysis populations

All analyses will be performed on the Full Analysis Set (FAS). The Full Analysis Set contains all patients enrolled into the trial.

## 11 Endpoints

### 11.1 Primary endpoint

The primary endpoint of the study is the occurrence of AKI within 72 h after extended surgery according to the KDIGO (Kidney Disease: Improving Global Outcomes) criteria (Table 3).

Stage	Serum creatinine	Urine output
1	$\geq 0.3$ mg/dl in 48 h or 1.5-1.9-times baseline within the last 7 days	$< 0.5$ ml/kg/h for $\geq 6$ h
2	2.0-2.9-times baseline	$< 0.5$ ml/kg/h for $\geq 12$ h
3	3-times baseline or $\geq 4.0$ mg/dl or initiation of RRT	$< 0.3$ ml/kg/h for $\geq 24$ h or anuria for $\geq 12$ h

Abbreviations: RRT, renal replacement therapy

Table 3: KDIGO criteria for the diagnosis of AKI.

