Key inclusion and exclusion criteria	
Inclusion criteria:
 
 
1. Age <math>\geq</math> 18 years
 
2. Major surgeries with a duration of at least 2 h
 
3. Planned or unplanned admission to the ICU, IMC or PACU after surgery
 
4. Written informed consent
 
 
Exclusion criteria:
 
 
1. Pre-existing AKI
 
2. AKI within the last 3 months
 
3. End stage renal disease with dialysis dependency
 
4. Kidney transplant
 

Study endpoints	
Primary endpoint: Occurrence of AKI within 72h after extended surgery according the KDIGO criteria.
 
Secondary endpoints: Secondary endpoints are:
 
 
• Use of renal replacement therapy
 
• Duration of AKI (transient vs. persistent)
 
• Length of ICU stay
 
• Length of hospital stay
 
• Survival 
 
◦ ICU mortality
 
◦ Hospital mortality
 
 
 
• MAKE90 (major adverse kidney events within 90 days): combined endpoint consisting of: 
 
◦ Mortality
 
◦ renal replacement therapy
 
◦ persistent renal dysfunction defined as serum-creatinine <math>\geq</math> 1.5 times as compared to baseline serum-creatinine
 
 
 
• Transition from non-AKI and AKI to CKD (i.e. development or progression; CKD defined by CKD-KDIGO) at day 90
 

Number of subjects	To be analyzed in the trial: n=10,000
Time plan	First patient first visit (FPFV): 01/06/2020 Last patient first visit (LPFV): 30/06/2022 Last patient last visit (LPLV): 30/09/2022 Final study report: 31/12/2022
Statistical analysis	
Statistical analyses will be performed according to the principles of the ICH-guideline E9 "Statistical Principles for Clinical Trials" using standard statistical software. Analyses will be performed based on the Full Analysis Set (FAS).
 
In the primary analysis the incidence of AKI will be estimated together with the exact corresponding two-sided 95% confidence interval according to Clopper-Pearson.

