### Secondary objectives:

The secondary objectives of the study are:

- to evaluate the severity and duration of post-surgery AKI, as well as the use of renal replacement therapy (RRT), all-cause mortality (ICU and hospital), ICU and hospital length of stay, and the occurrence of MAKE (major adverse kidney events) and CKD (chronic kidney disease) development or progression up to 90 days after extended surgical procedures,
- to determine the effects of pre- and intraoperative factors on the occurrence of AKI,
- to determine the association between AKI and postoperative outcomes including use of RRT, all-cause mortality, ICU and hospital length of stay, and the occurrence of MAKE up to 90 days after extended surgical procedures.
- Transition from non-AKI and AKI to CKD (i.e. development or progression; CKD defined by CKD-KDIGO) at day 90.

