## 6 General study design and plan

The EPIS-AKI trial is an international, prospective, observational, multi-center, cross-sectional cohort study including patients that undergo extended surgical procedures.

[figure not shown]

Figure 1: Trial workflow.

Eligible patients, i.e. meeting all inclusion and none of the exclusion criteria, will be enrolled into the study (Figure 1). The visit plan is shown in Table 1.

Visit	S	B	OD	POD 1-3	Day 90
Inclusion and Exclusion criteria	X				
Demography Age, gender, race, height, weight, creatinine, comorbidities, ASA status, medication		X			
Admission diagnosis, source of admission		X			
Intraoperative data Surgical procedure (speciality, type, duration, if cardiac: CPB)			X		

/ aortic X-clamp duration), fluid status (fluid intake, transfusion, blood loss, urine output), use of cell saver, episodes of hypotension, drug application, intraoperative complications					
Postoperative data APACHE, SAPS, fluid status, drug application, postoperative complications				X	
AKI Stage, occurrence, duration, diagnosis, RRT				X	
Concomitant Medication Vasopressors, nephrotoxic agents, diuretics				X	
Mortality					X
Length of primary stay (ICU, Hospital)					X
Serum-creatinine					X
Renal recovery					X
Number of days of RRT/RRT dependence					X
MAKE (major adverse kidney events)					X

Abbreviations: S, Screening; B, Baseline, OD, operative day; POD, postoperative day; ASA, American Society of Anaesthesiology; CPB, cardiopulmonary bypass; APACHE, Acute Physiology And Chronic Health Evaluation; SAPS, Simplified Acute Physiology Score; AKI, Acute Kidney Injury; RRT, Renal Replacement Therapy; ICU, intensive care unit.

Table 1: Visit plan.

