### 12.3 Secondary analyses

All secondary analyses are considered exploratory.

Secondary outcomes (see 11.2) will be evaluated based on descriptive statistics, point estimates and corresponding 95% confidence intervals.

To detect factors that might be correlated to the occurrence of AKI, MAKE90, CKD90 (i.e. development or progression), and a persistent AKI, exploratory uni- and multivariable logistic regression analyses will be conducted (including age, arterial hypertension, diabetes mellitus, sex, type of surgery as explanatory variables).

The association between AKI (overall and by severity, duration) and postoperative outcomes including use of RRT, all-cause mortality, ICU and hospital length of stay, the occurrence of MAKE90, the development or progression of CKD90, and the estimated glomerular filtration rate (eGFR) at day 90 will be assessed descriptively. Subsequent analyses for related risk factors will be undertaken.

The impact of baseline serum-creatinine and urinary output on the occurrence of MAKE90 in patients with post-surgical AKI will be assessed by logistic regression analyses.

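### The exploratory AKI models in SAP 12.3 name no body-size term although the urine-output criterion is scaled per kg, so the diabetes and hypertension odds ratios can be biased upward

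*SAP*

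**What the plan says.** SAP 11.1 sets the endpoint: "The primary endpoint of the study is the occurrence of AKI within 72 h after extended surgery according to the KDIGO" criteria. Table 3 gives a creatinine column and a urine-output column. The stage 1 urine-output entry is "< 0.5$ ml/kg/h for $\geq 6$ h", and the other urine-output rates in the table are also per kg.

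SAP 12.3 specifies uni- and multivariable logistic models for AKI, MAKE90, CKD90 and persistent AKI, "including age, arterial hypertension, diabetes mellitus, sex, type of surgery as explanatory variables". Their purpose is put as "To detect factors that might be correlated to the occurrence of AKI" and the other outcomes. The same section states: "All secondary analyses are considered exploratory". The objective behind the models, in SAP section 5, is worded more strongly: "to determine the effects of pre- and intraoperative factors on the occurrence of AKI".

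Body size is available. The visit plan in SAP section 6 lists "Age, gender, race, height, weight, creatinine, comorbidities, ASA status, medication" at baseline, and 11.3.2 repeats height and weight among the variables to be described. No body-size term is named for any model in the synopsis, in 12.3 or in the subgroup section 12.5.

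**The concern.** An omitted covariate in an exploratory model is usually a minor matter. Here the omitted variable sits in the denominator of the outcome. The stage 1 cut-off is 0.5 × weight in ml/h, so a heavier patient must produce more urine to avoid the diagnosis. If output does not rise in the same proportion, heavier patients meet the criterion more often by construction, and any named covariate that goes with weight takes up part of that excess. Diabetes and hypertension are the obvious candidates among the five named.

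The risk is a definitional artefact reported as a preoperative risk factor. SAP 12.4 calls two-sided p-values of 0.05 or less statistically noticeable, and at the planned sample size ("To be analyzed in the trial: n=10,000") even a modest odds ratio can reach that level.

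**Working it through.** **The plan's own figure.** The only planning figure is the width of the exact 95% interval at n = 10,000 and 40% AKI, given as 0.019 in SAP section 8. With 4,000 events the Clopper-Pearson limits are 0.3904 and 0.4097, a width of 0.0193. It reproduces and is not in dispute.

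**Cut-off by weight (from Table 3).** 0.5 × weight gives 30 ml/h at 60 kg, 40 at 80 kg, 50 at 100 kg and 60 at 120 kg.

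**Assumptions (none is in the SAP).**
- Height 170 cm; ideal weight 50 + 0.91 × (170 − 152.4) = 66.0 kg.
- Heavy patient at BMI 35: 35 × 1.70² = 101.15 kg. Cut-offs: 33.0 ml/h lean, 50.6 ml/h heavy.
- Six-hour output is lognormal with log-SD 0.5 and median 0.9 × 66 × (w/66)^a ml/h, where a = 0 (no scaling with weight), 0.5 (half) or 1 (full).
- 40% of diabetic and 20% of other patients are at BMI 35; the rest are at ideal weight. Diabetes has no true effect.
- A share c of patients has AKI by creatinine, independently of weight and diabetes.

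**Step 1, oliguria.** P = Φ([ln(cut-off) − ln(median)]/0.5).
- Lean: Φ(ln(33.0/59.4)/0.5) = 0.120 for every a.
- BMI 35: 0.374 (a = 0), 0.227 (a = 0.5), 0.120 (a = 1).

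**Step 2, mix by diabetes status.**
- a = 0: diabetic 0.4 × 0.374 + 0.6 × 0.120 = 0.221; other 0.2 × 0.374 + 0.8 × 0.120 = 0.171.
- a = 0.5: 0.163 and 0.141.

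**Step 3, AKI by either criterion.** P(AKI) = 1 − (1 − c)(1 − P(oliguria)). At c = 10% and a = 0 this is 0.299 and 0.254, so the odds ratio is (0.299/0.701)/(0.254/0.746) = 1.26 before rounding of inputs.

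| Creatinine AKI (c) | No scaling | Half scaling | Full scaling |
|---|---|---|---|
| 0% (oliguria alone) | 1.38 | 1.18 | 1.00 |
| 10% | 1.26 | 1.11 | 1.00 |
| 20% | 1.19 | 1.08 | 1.00 |
| 30% | 1.16 | 1.06 | 1.00 |

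**Second check, continuous weight.** A simulation of 1,000,000 patients per scenario used mean weight 78 kg, SD 16 kg, 10% creatinine AKI and true odds ratios of 1. The models contained diabetes and hypertension, without and then with weight. Monte Carlo error is about ±0.02.

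| Extra kg (diabetes / hypertension) | No scaling: OR diabetes / hypertension | Half scaling |
|---|---|---|
| 2 / 2 | 1.03 / 1.06 | 1.02 / 1.03 |
| 5 / 4 | 1.12 / 1.08 | 1.07 / 1.04 |
| 10 / 8 | 1.25 / 1.21 | 1.12 / 1.10 |

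With full scaling every odds ratio was about 1.00. With weight in the model both odds ratios lay between 0.98 and 1.01 in every scenario.

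**What n = 10,000 would flag.** Assume 20% diabetic patients, that is 2,000 against 8,000. SE(log OR) = √[1/(2,000·p(1−p)) + 1/(8,000·p(1−p))]. This is 0.0625 at AKI rate p = 20% and 0.0510 at 40%. Odds ratios of exp(1.96 × SE) = 1.13 and 1.11 would then reach p ≤ 0.05, so the upper part of the range above could be flagged.

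**The case against.** **Table 3 is the consensus definition the trial set out to use.** This stands. A reader might infer that AKI incidence is overstated in obese patients, or that the per-kg cut-off is a mistake. The documents support neither: the primary objective is incidence by KDIGO, and the Clopper-Pearson analysis in 12.2 uses no covariates. The point concerns the models only.

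**The artefact is conditional.** This stands too. A reader might take it as certain that heavy patients count as oliguric at normal output. The SAP gives no normal absolute output, no weight difference by diabetes or hypertension, and no share of AKI resting on urine output alone. With full scaling the bias is nil.

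**The larger odds ratios are for oliguria alone.** It is tempting to quote 1.38 and 1.18 as the bias in AKI. AKI in Table 3 is creatinine or urine output, and creatinine cases unrelated to weight dilute the effect, as the table shows. The two-point weight distribution is also crude; with continuous weight and differences of 2 to 5 kg, the diabetes odds ratio is only 1.02 to 1.12 with half or no scaling.

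**The model list may be open, and the models are exploratory.** The list in 12.3 is introduced by *including*, the synopsis mentions further candidates such as length of surgery, and 12.4 allows later analyses. Nothing forbids BMI. This lowers the weight of the point but does not remove it: 12.3 holds the only explicit covariate list for these models, and a variable built into the outcome definition should not be left to a choice made after the data are seen.

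**The SAP does not say which weight is the divisor.** The protocol or the data-collection instrument, neither of which is at hand, may settle that. It is not raised as a defect.

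**Conclusion.** The point holds for the exploratory models in 12.3 and the subgroup models in 12.5. As named, the covariates leave out body size while the outcome is partly scaled by it, so the diabetes and hypertension odds ratios for AKI can be biased upward with no renal effect. With 10% independent creatinine AKI, the spurious diabetes odds ratio runs from 1.00 (full scaling) through 1.11 (half) to 1.26 (none), and it shrinks as the creatinine share grows.

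The size rests wholly on assumed scaling, weight differences and event rates; the direction rests on output rising less than in proportion to weight and on these patients being heavier. The bias is therefore possible and modest, not demonstrated. The primary analysis is unaffected. A change is still worth making because the correction is specific and almost free.

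**What to change.** 1. In 12.3, add BMI, calculated from the height and weight already collected, as an explanatory variable in the models for AKI and persistent AKI. Do the same in the 12.5 subgroup models.
2. Repeat the 12.3 AKI model once, as a sensitivity analysis, with AKI defined by the creatinine criterion alone. A diabetes or hypertension odds ratio that is clearly smaller there than in the main model without BMI would be compatible with the artefact.
3. State in 12.3 that the BMI coefficient mixes a definitional effect with any real one and is not to be read as a causal effect of obesity.

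The cost is one model term and one extra model, with no new baseline data. The downside is the mixed meaning of the BMI coefficient, which item 3 covers. The primary endpoint, Table 3 and the sample size stay as they are.

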### 11.2 Secondary endpoints

- Severity of post-surgery AKI
- Duration of AKI (transient, < 48h vs. persistent, > 48h)
- Use of renal replacement therapy (RRT) within 90 days after extended surgery
- All-cause mortality 90-days after extended surgery
- Length of ICU stay (time from ICU admission until ICU discharge)
- Length of hospital stay (time from hospital admission until hospital discharge)
- Occurrence of MAKE (major adverse kidney event), defined as combined endpoint consisting of
  - o all-cause mortality,
  - o use of RRT,
  - o persistent renal dysfunction defined as serum-creatinine  $\geq 1.5$  times as compared to baseline serum-creatinine within 90 days after extended surgery (MAKE90)
- Transition from non-AKI and AKI to CKD G3 to G5 (i.e. development or progression; CKD defined by CKD-KDIGO, Table 4) at day 90 (CKD90)

Stage	eGFR [mL/min/1.73m  ]
G1	$\geq 90$
G2	60-89
G3a	45-59
G3b	30-44
G4	15-29
G5	< 15

Abbreviations: eGFR, estimated glomerular filtration rate

Table 4: KDIGO classification for the diagnosis of CKD.

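### RRT started within 72 h defines stage 3 AKI and also counts as an event in use of RRT and MAKE90, so a part of their planned descriptive association is built in

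*SAP*

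**What the plan says.** Three parts of the SAP meet here.

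- **AKI (section 11.1, Table 3).** AKI is assessed over the 72 h after surgery. One route to stage 3 reads "mg/dl or initiation of RRT", so starting RRT is enough by itself.
- **Outcomes (section 11.2).** One secondary endpoint is "Use of renal replacement therapy (RRT) within 90 days after extended surgery". MAKE90 is a composite of death, use of RRT and persistent renal dysfunction; the synopsis gives its window as "major adverse kidney events within 90 days): combined endpoint consisting of". Neither endpoint excludes RRT begun in the first 72 h.
- **Analysis (section 12.3).** The plan is: "The association between AKI (overall and by severity, duration) and postoperative outcomes including use of RRT", with MAKE90 among the outcomes listed. The sentence ends "eGFR) at day 90 will be assessed descriptively". Section 10 puts every enrolled patient in every analysis. No 72 h landmark and no separate handling of early RRT is stated.

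The association is a stated secondary objective in section 5: "to determine the association between AKI and postoperative outcomes including use of RRT", with MAKE also named.

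**The concern.** A patient who starts RRT within 72 h of surgery is, from that one event, a stage 3 AKI patient, a use-of-RRT event and a MAKE90 event. The non-AKI, stage 1 and stage 2 groups can contain no RRT from that period, because any such patient is moved to stage 3. To that extent the tables relate a criterion to itself.

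What is at stake is interpretation. A rise in RRT use and MAKE90 from no AKI to stage 3 is easily read as prognosis. From the planned tables a reader cannot tell how much of it comes from the definition and how much from the later course.

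**Working it through.** **The plan's own figures.** The SAP gives no expected rate of RRT, stage 3 AKI or MAKE90, so there is no figure to reproduce on this point. From section 8 come only n = 10,000 and a planning AKI rate of 40%, which gives 0.40 × 10,000 = 4,000 AKI patients. All other inputs below are assumptions.

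**Which patients carry the definitional part.** Someone who already met the creatinine or urine-output criteria and then needed RRT is genuine AKI followed by RRT. Only patients who reach AKI, or stage 3, through RRT alone add a purely definitional link. Table 3 leaves that route open for stage 3: by urine output, stage 3 needs 24 h of oliguria or 12 h of anuria ("h or anuria for" 12 h). If urine output is counted from the end of surgery, RRT begun in the first 12 h can be stage 3 at that moment only by creatinine or by the RRT itself.

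**Model.** Let later risk x be the same in all groups, so the true risk ratio (RR) is 1. Let p be the share of the AKI group (or of stage 3) placed there by RRT alone:

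- AKI overall: p = e × g, where e is the share of AKI patients with RRT within 72 h and g is the share of those with RRT as sole criterion.
- Stage 3: p = f × h, with the same meanings within stage 3.
- Apparent RR = (p + (1 − p)x) / x = p/x + (1 − p).

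**Central illustration.** e = 0.02, g = 0.20, so p = 0.004 (of 4,000 AKI patients, 80 have early RRT and 16 of these have RRT as sole criterion).

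- Use of RRT, x = 0.01: 0.004/0.01 + 0.996 = 1.396, about **1.40**.
- MAKE90, x = 0.05: 0.004/0.05 + 0.996 = 1.076, about **1.08**.

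**Ranges.** Assumed: e 0.5–5%, f 10–50%, g and h 10–50%, later RRT risk 0.5–1%, other MAKE90 risk 5–10%.

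| Contrast | Low end | High end |
|---|---|---|
| Use of RRT, AKI vs non-AKI | p = 0.0005, x = 0.01: 0.05 + 0.9995 = 1.05 | p = 0.025, x = 0.005: 5 + 0.975 = 5.98 |
| MAKE90, AKI vs non-AKI | p = 0.0005, x = 0.10: 0.005 + 0.9995 = 1.00 | p = 0.025, x = 0.05: 0.5 + 0.975 = 1.48 |
| MAKE90, stage 3 vs non-AKI | p = 0.01, x = 0.10: 0.1 + 0.99 = 1.09 | p = 0.25, x = 0.05: 5 + 0.75 = 5.75 |

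**Cross-check by counts.** In the central illustration the planned table for use of RRT would show (80 + 39.2)/4,000 = 2.98% against 1.00%, RR 2.98. Setting aside only the 16 sole-criterion patients gives (64 + 39.2)/3,984 = 2.59%, RR 2.59. The difference, 0.39, agrees with the excess of about 0.40 from the formula. For MAKE90 the same steps give (80 + 196)/4,000 = 6.90%, RR 1.38, and (64 + 196)/3,984 = 6.53%, RR 1.31; the difference is 0.07.

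**The case against.** The strongest reply is that RRT after AKI is a real consequence, that the study follows the consensus definition it chose, and that section 12.3 calls all secondary analyses exploratory. Much of this stands.

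- **Not all early RRT is definitional.** A reader might infer that every RRT start within 72 h is circular. On the same inputs with g = h = 1 that would give RRs of 1.5–11 for use of RRT, 1.05–1.95 for MAKE90 and 1.9–10.5 for MAKE90 in stage 3. The SAP does not support this: Table 3 has creatinine and urine-output routes, and patients who met them first are true AKI with a true outcome. In the illustration that is 64 of 80, so the RR of 2.98 is mostly not an artefact of definition.
- **The sole-criterion share has no source in the SAP.** The 12 h argument concerns stage 3 only. AKI overall needs just 6 h of oliguria or a 0.3 mg/dl rise. Section 11.3.6 also lists worst-case AKI, and urine-output criteria may still be met later in the 72 h. At the low end the overall effect is negligible.
- **Part of the picture is already reported.** Use of RRT and 90-day mortality are endpoints in their own right, the start of and indication for RRT are described, and section 12.4 allows further exploratory analyses.
- **The creatinine component of MAKE90.** Section 11.2 words it as "times as compared to baseline serum-creatinine within 90 days after extended surgery", from which a reader might infer a second overlap with the creatinine criterion for AKI. The word persistent and the Day 90 column of Table 1 point to the day-90 value, so this is at most a separate wording matter.

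What does not fall is the overlap itself. It follows from the definitions whatever inputs are assumed, and no planned table separates it.

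**Conclusion.** The point holds in a limited form. RRT started within 72 h sits on both sides of the planned association of AKI with use of RRT and with MAKE90. The built-in part is larger for stage 3 than for AKI overall, and larger for use of RRT than for MAKE90.

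Its size cannot be taken from the SAP. The illustrative RRs of about 1.40 and 1.08, and the ranges around them, rest on assumed rates and on equal later risk in all groups. They show what the definition alone could produce and do not predict the study's results.

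Primary incidence, mortality, length of stay, CKD90 and day-90 eGFR are not affected by this overlap. Because the analysis is descriptive and exploratory, this is a minor, optional improvement.

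**What to change.** In section 12.3, keep the planned tables. For use of RRT and MAKE90 only, add one table labelled as supplementary:

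- Patients whose RRT began within 72 h form a separate row, split by whether they also met a creatinine or urine-output criterion. State whether this means before RRT began or at any time in the 72 h.
- For all other patients, only RRT started after 72 h counts as the RRT event. No restaging is needed, because everyone who could reach AKI or stage 3 through RRT is already in the separate row.
- Report the MAKE90 components separately, including RRT dependence at day 90.

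The cost is a short text change, a derived variable for RRT start within 72 h, the split of that row, and one table. Start of RRT is listed in section 11.3.6; RRT dependence and creatinine at day 90 are in Table 1. The split also needs to know which criterion was met. Section 11.3.6 lists the AKI diagnosis, but the SAP does not say whether each criterion is recorded, so this should be checked.

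The downsides are slightly more exploratory output and small numbers in the early-RRT row. The supplement also sets aside genuine early RRT events, so it complements the planned analysis and does not replace it.

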### Inclusion criteria:

1. Age  $\geq$  18 years
2. Major elective or emergency surgery procedures with a duration of at least 2h
3. Planned or unplanned admission to the ICU, IMC or PACU after surgery
4. Informed Consent

Major surgeries will be targeted within the broad subgroup domains of neurosurgery, cardiac, vascular, gynecology, thoracic, urology, orthopedics/trauma and abdominal surgery.

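### Hospital length of stay is counted from hospital admission, so days before surgery enter an outcome that the SAP treats as postoperative and relates to AKI

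*SAP*

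**What the plan says.** Section 11.2 of the SAP fixes the two stays as follows:

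- "Length of hospital stay (time from hospital admission until hospital discharge"
- "Length of ICU stay (time from ICU admission until ICU discharge"

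Section 5 (secondary objectives) sets out "to determine the association between AKI and postoperative outcomes including use of RRT, all-cause mortality, ICU and hospital length of stay". Section 12.3 repeats this as an analysis: "The association between AKI (overall and by severity, duration) and postoperative outcomes including use of RRT, all-cause mortality, ICU and hospital length of stay", among other outcomes, "will be assessed descriptively". The same section states: "All secondary analyses are considered exploratory".

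Three other provisions bear on the reading. Section 7 requires "Planned or unplanned admission to the ICU, IMC or PACU after surgery", admits both elective and emergency procedures, and excludes pre-existing AKI. Section 10 analyses every enrolled patient. Section 14.1 rules out imputation. No section says how a patient who dies in the ICU or in hospital enters either length of stay.

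**The concern.** The exposure, AKI, is counted within 72 h after surgery, and patients who already have AKI are excluded. Time in hospital before the operation therefore cannot result from the exposure, yet under section 11.2 it is part of the outcome. In the same list, RRT, mortality and MAKE are timed from surgery, so the hospital-stay clock also departs from the SAP's own anchor.

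At stake is the meaning of the AKI comparison for hospital stay, which serves a named secondary objective. If AKI and non-AKI patients waited different lengths of time for their operation, that difference would be reported as part of the association between AKI and stay. A sample of 10,000 makes such a figure more precise but does not remove the distortion. Section 12.3 plans a descriptive comparison here and names no adjustment that could remove it.

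The missing rule for deaths is a second, related matter. Depending on what is done with stays that end in death, the same table answers different questions.

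**Working it through.** **The plan's own figure.** The SAP states no figure for length of stay. Its only planning figure is the width of the exact 95% interval, 0.019, at 40% incidence and n = 10,000 (section 8). With 4,000 events in 10,000, the Clopper-Pearson limits are 0.3904 and 0.4097, a width of 0.0193. This agrees with the stated figure, and length of stay plays no part in it.

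**Hospital stay: the identity.** Write hospital stay as H = P + S, with P the days from admission to surgery and S the days from surgery to discharge. For means,

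difference in H (AKI minus no AKI) = difference in S + difference in P.

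The second term is unrelated to any effect of AKI and enters at full size. The identity is exact for means. Section 12.1 also reports medians and quartiles, for which the shift is not exactly additive.

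**Illustration.** All inputs are assumed: mean S of 14 days with AKI and 10 days without, a true difference of 4 days and a ratio of 14/10 = 1.40.

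| Mean P, no AKI | Mean P, AKI | Difference in H | Ratio of means |
|---|---|---|---|
| 1 | 1 | 15 - 11 = 4 | 15/11 = 1.36 |
| 2 | 2 | 16 - 12 = 4 | 16/12 = 1.33 |
| 1 | 2 | 16 - 11 = 5 | 16/11 = 1.45 |
| 2 | 4 | 18 - 12 = 6 | 18/12 = 1.50 |
| 4 | 2 | 16 - 14 = 2 | 16/14 = 1.14 |

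A simulation of 1,000,000 patients with 40% AKI gave differences of 3.98, 3.97, 4.98, 5.97 and 1.98 for these rows. Equal preoperative stays leave the difference unbiased but dilute the ratio.

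The gap can also be built from the share of patients who wait: (share in AKI - share in no AKI) x days waited. Assumed values give (0.30 - 0.20) x 4 = 0.4, (0.40 - 0.20) x 4 = 0.8 and (0.50 - 0.20) x 7 = 2.1 days. With the shares exchanged between the groups, the same values carry a minus sign.

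**ICU stay.** Section 11.2 starts the clock at ICU admission. Section 7 places the qualifying unit admission after surgery. Read together, the ICU clock normally starts after the operation. Preoperative ICU days can enter only for patients already in an ICU beforehand, whom the SAP does not address.

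**Deaths.** Both definitions end at discharge and do not mention death. Two readings fit the text.

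- *Death is entered as the end of the stay.* Within one group, if survivors stay 12 days and 20% die at day 6, the mean is 0.8 x 12 + 0.2 x 6 = 10.8 instead of 12.0. For a between-group figure, assume S is gamma with shape 2 and scale θ (7 with AKI, 5 without) and that the 14 and 10 days above apply. Assume also that patients who die have an exponential death time with mean 5 days. The mean stay of those selected to die is 1/a + (1/θ)/a², with a = 1/θ + 1/5. That gives 4.13 days with AKI and 3.75 without. The differences are then:
  - deaths 5% vs 1%: (0.95 x 14 + 0.05 x 4.13) - (0.99 x 10 + 0.01 x 3.75) = 3.57
  - deaths 10% vs 2%: (0.90 x 14 + 0.10 x 4.13) - (0.98 x 10 + 0.02 x 3.75) = 3.14
  - deaths 20% vs 2%: (0.80 x 14 + 0.20 x 4.13) - (0.98 x 10 + 0.02 x 3.75) = 2.15

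  The simulation gave 3.55, 3.13 and 2.14.
- *A patient who dies has no discharge time.* The value is missing, is not imputed, and the summary covers those discharged alive. The simulation then returned 3.98 to 3.99 days, but only because death was drawn independently of the underlying stay. Real data need not behave so.

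**The case against.** The best defence is that little hangs on this. The analysis is exploratory and descriptive, mortality is set against AKI in the same sentence of section 12.3, and admission-to-discharge is a familiar measure of resource use. All of this stands, and it limits the weight of the point. It does not reconcile an admission-based clock with a stay that sections 5 and 12.3 call postoperative.

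Three stronger readings are tempting, and the SAP does not support them.

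- *A reader might infer that AKI will look worse than it is.* That would need AKI patients to wait longer before surgery. The SAP gives no such figures. Emergency surgery is eligible, and emergency patients could combine a short wait with a high AKI risk, which reverses the sign.
- *A reader might infer that ICU stay suffers in the same way.* The qualifying admission follows surgery, so this is confined to patients already in an ICU, whose number is unknown.
- *A reader might infer that the SAP counts death as discharge.* It names discharge only and says nothing about death. A convention may sit in the protocol or the case report form guidance, neither of which is shown. This part is therefore an open rule, not a stated error.

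**Conclusion.** The point holds for hospital stay. The stated definition includes time before the exposure, although the stay is analysed as a postoperative outcome of AKI. Any gap in mean preoperative stay passes one-for-one into the difference in means, in either direction. The SAP offers nothing from which to estimate the gap, and every size shown above rests on assumed inputs. If preoperative stay is equal in the two groups, the difference in means is unbiased.

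For ICU stay, a clarification is enough. For deaths, the SAP leaves the rule open. Treating death as discharge would shorten stays in the group with more deaths, provided that deaths come before the patients would otherwise have left, but the document does not say that this will be done.

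This is a cheap improvement to an exploratory secondary analysis. The primary incidence estimate and the sample size are unaffected.

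**What to change.** In sections 11.2 and 12.3:

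- For the association with AKI, define hospital stay from the index surgery to hospital discharge. Keep the admission-based stay as a separate descriptive line.
- Specify that ICU stay means the first postoperative ICU stay.
- State how deaths enter both stays. Either report stay among patients discharged alive next to the proportion who died, by AKI status, or analyse time to discharge alive with death as a competing event.

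The cost is mainly wording, with two reservations. The surgery-based figure is less comparable with reports that count from admission. It also needs surgery, discharge and death dates. The visit plan (section 6, Table 1) lists lengths of stay and mortality rather than dates. The 72 h endpoint requires the time of surgery, so the dates are probably held, but this should be confirmed before the text is changed.
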